I agree to ensure that the confidential information contained in this document will not be used for any purpose other than the evaluation or conduct of the clinical investigation without the prior written consent of Ionis Pharmaceuticals, Inc.

Investigator's Signature	 
Investigator's Name (please print)	Date (DD Month YYYY)

SUMMARY OF ADDENDUM

CONFIDENTIAL

Protocol Number: ISIS 420915-CS3

Protocol Title: An Open-Label Extension Study to Assess the Long-Term Safety and

Efficacy of ISIS 420915 in Patients with Familial Amyloid

Polyneuropathy (FAP)

Protocol Amendment: 5 **Addendum Number:** 1

Addendum Date: 13 May 2020

Due to the COVID-19 pandemic, patients participating in ISIS 420915-CS3 may be prevented from attending study visits at study centers because of the policies of the centers (or the institution in which they are located), governmental restrictions on movement, or a patient's desire to minimize risk of infection.

In ISIS 420915-CS3, visits to study centers are required only for the study visits in Week 24 and Week 52 of Treatment Years 2, 3, 4, and 5 (all current study participants have progressed past Year 1). Therefore, the Sponsor issued guidance, on 17 March 2020, to the study centers with patients actively participating in ISIS 420915-CS3 that the Week 24 and Week 52 visits may be conducted remotely. The memorandum is attached as Appendix A.

Briefly, when patients do not attend on-site Week 26 or Week 52 visits, telephone contact between site staff and patients is required to collect adverse event and concomitant medication usage information and to assess the patients' general well-being. Collection of specimens for serum chemistry, hematology, and urinalysis is also required. Where possible, collection of specimens for the other laboratory tests specified for the visit are also to be collected.

Protocol

APPENDIX A. MEMORANDUM TO STUDY INVESTIGATORS AND SITE PERSONNEL

MEMORANDUM

To: Tegsedi ISIS 420915-CS3 ARG and BRA Study Investigators and Site Personnel

From: Ionis Clinical Management Team

RE: Study Modifications due to Coronavirus or COVID-19

Date: 17 MAR 2020

Given the rapid spread of the Coronavirus, or COVID-19, it is critical that we do our best to mitigate the impact of this outbreak, prevent illness, and ensure patient safety while patients are participating in ISIS 420915-CS3.

lonis understands the need for flexibility and modifications during this time of heightened COVID-19 risk. For the next month, and continuing on a month by month basis:

- All study visits including the semi-annual visits required to be on-site (Wk 26 and 52) by the protocol may be conducted remotely.
- In place of the semi-annual required on-site visits (Wk 26 and 52),
 - We require a telephone contact with the patient(s) to collect AE(s) and conmed usage information and to assess the patient's general well-being.
 - We require collection of specimens for serum chemistry, hematology, and urinalysis.
 - Where possible, we ask for collection of specimens for the other laboratory tests [thyroid panel, the coagulation panel (PT, aPTT, INR), retinol, hs-CRP, PD panel, NT-proBNP, immunogenicity, and trough PK] if specified by protocol.
- For the Wk 13 and 39 visits and all of the Additional Visits, the protocol specified collections should be performed.
- Should a patient report any symptoms that are concerning, the PI can triage the patient accordingly.
- Protocol Deviations will need to be entered for any efficacy measure not performed due to the COVID-19 outbreak.

Ionis will continue to assess these modifications and will update this guidance on a monthly basis as we monitor the COVID-19 outbreak. Please escalate any concerns to the Clinical Study Management Team, as we continue to stay in operation.

ionispharma.com

[name]

[contact]

From:

Sent: Tuesday, March 17, 2020 11:58 AM

To:

- Centro de Pesquisa Clfnica (Lar

- Centro de Pesquisa Clinica (Lar Escola)

Cc:

(Contractor); (Contractor); (Contractor);

(Contractor);

Subject:

Iorns CS3 COVID-19 memo

Attachments:

TTR-CS3-COVID-19 Memo_17_Mar_2020.pdf

Importance:

High

Dear Dr.• , Dr,_

and Dr.•

Please see the attached memo from Ionis regarding the recent corona virus outbreak and instructions regarding the CS3 study and future patient visits.

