Appendix A Schedule of Procedures Continued

	Screen							Υ	ear 1							Ye	ar 2			Y	ear3	
	1	W	W	W	W	W	W	W	W	W	W	W	W	W	W	W	W	W	W	W	W	W
Study Week	:S 4 weeks [⊥]	1	4	7	10	13	15	18	21	23	26	29	39	52	65	78	91	104	117	130	143	156
		D	D	D	D	D	D	D	D	D	D	D	D	D	D	D	D	D	D	D	D	D
Study Day	S-28 to S-1	1	22	43	64	85	99	120	141	155	176	197	267	358	449	540	631	722	813	904	995	1086
Visit Window(+/- Days)		0	7	7	7	7	7	7	7	7	7	7	7	7	10	10	10	10	10	10	10	10
Labs																						
Pregnancy Test ⁷ ·A	х3	X		X		X					X			X		X	XS	X	XS	X	XS	X
Chemistry PanelA(fasting)	хЗ	X	XS	X	XS	X	XS	XS	XS	XS	X	XS	XS	X	XS	X	XS	X	XS	X	XS	X
Additional Platele 1 ta 3 nd Serum Creatinine		x3 X XS X XS XS XS XS XS XS X X X X X X X X X X X X X																				
HematologI	хЗ	X	XS	X	XS	X	x8	XS	XS	XS	X	XS	XS	X	XS	X	XS	X	XS	X	XS	X
UrinalysisA	х3	X	XS	X	XS	X	x8	XS	XS	XS	X	XS	XS	X	XS	X	XS	X	XS	X	XS	X
24 hour Urine (serum creatinine required) ⁹	X																					
Thyroid PanelA	х3			X		X					X			X		X		X				X
PT, aPTT, INRA	х3			X		X					X			X		X		X				X
RetinolA(fasting)		X		X		X					X			X		X		X		X		X
hs-cRpA		X		X		X					X			X		X	XS	X	XS	X	XS	X
PD PanelA(fasting)		X		X		X		XS	XS		X		XS	X	XS	X	XS	X	XS	X	XS	X
NT-proBNPA		X		X		X		XS			X		XS	X	XS	X	XS	X	XS	X	XS	X
Immunogeniciif				X		X		XS			X		XS	X	XS	X	XS	X	XS	X	XS	X
PK TroughA		X		X		X		XS			X		XS	X	XS	X	XS	X	XS	X	XS	X

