Appendix B List of Laboratory Analytes

Appendix B List of Laboratory Analytes

Clinical Chemistry	Screening Tests	Hematology	Inflammatory
Panel	• FSH (women only)	Red blood cells	• Hs-CRP
• Sodium	• Serum βhCG	Hemoglobin	
• Potassium	Urine hCG	Hematocrit	Urinalysis ¹
• Chloride		• Platelets	• Color
Bicarbonate	Coagulation	White blood cells	Appearance
• Total protein	• aPTT (sec)	• WBC Differential (%	Specific gravity
• Albumin	• PT (sec)	and absolute)	• pH
• Calcium	• INR	 Neutrophils 	 P/C and Alb/C Ratios
• Magnesium		 Eosinophils 	• Protein
• Phosphorus	PD Panel ¹	 Basophils 	• Blood
• Glucose	Transthyretin	 Lymphocytes 	• Ketones
• BUN	 Retinol binding 	 Monocytes 	Urobilinogen
• Creatinine	protein 4 (RBP4)		Glucose
• Uric Acid		Thyroid Panel	Leukocyte esterase
Total bilirubin	24-hour Urine ⁴	• TSH	Nitrate
• Direct (conjugated)	• Creatinine	• Free T4 (FT4)	Microscopic
bilirubin	• Protein		examination ³
• Indirect	• Albumin	Pharmacokinetics ²	
(unconjugated) bilirubin		• ISIS 420915 levels in	
• ALT	Other	plasma	
• AST	• Retinol ¹		
Alkaline phosphatase	 Retinyl Palmitate 		
Arkanne phosphatase Creatine kinase	• NT-proBNP ¹		
Estimated creatinine	• Immunogenicity		
clearance (CKD-EPI)	(anti-ISIS 420915 antibodies)		
• Total IgG	announcs		
• Total IgM			
5			

- 1 Other biomarkers may be measured at the discretion of the Sponsor. Back-up samples will be collected and stored. For transthyretin and retinol, back-up samples may be analyzed in more sensitive transthyretin or retinol assays at the discretion of the Sponsor. Back-up urine samples may be analyzed for additional renal biomarkers
- 2 Plasma PK samples may also be used for profiling of drug binding proteins, bioanalytical method validation purposes, stability assessments, metabolite assessments, or to assess other actions of ISIS 420915 with plasma constituents
- Will be performed on abnormal findings (if the initial analysis is positive for protein, blood, nitrite, &/or leukocyte esterase) unless otherwise specified (to include: casts, crystals, bacteria, epithelial cells, RBC, WBC, yeast)
- 4 Serum creatinine blood draw required

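### For remote Week 26/52 visits the COVID-19 memo leaves out the scheduled serum βhCG pregnancy test, and the addendum asks for it only where feasible; it should be a required specimen

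*Combined protocol and SAP*

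**What the plan says.** The Schedule of Procedures (protocol Appendix A) has a "Pregnancy Test" row with a mark at every Week 26 and Week 52 visit of Years 2 to 5. Footnote 7 limits it to females of childbearing potential and specifies serum βhCG after Day 1. The list of analytes (protocol Appendix B) places "Serum βhCG" under Screening Tests, apart from the chemistry panel and urinalysis.

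The memo of 17 March 2020, addressed to the Argentine and Brazilian sites, lets Week 26/52 visits be held remotely. It puts laboratory work in three tiers:

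- Required: "We require collection of specimens for serum chemistry, hematology, and urinalysis".
- Requested where feasible: "the other laboratory tests [thyroid panel, the coagulation panel (PT, aPTT, INR), retinol, hs-CRP, PD panel, NT-proBNP, immunogenicity, and trough PK".
- Unchanged: "For the Wk 13 and 39 visits and all of the Additional Visits, the protocol specified collections should be performed".

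The sponsor adds that it "will update this guidance on a monthly basis as we monitor the COVID-19 outbreak".

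The addendum of 13 May 2020 keeps the same three required specimens and then says: "Where possible, collection of specimens for the other laboratory tests specified for the visit are also to be collected". It continues to rely on the memo: "The memorandum is attached as Appendix A".

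**The concern.** The two memo lists read as a complete inventory of the visit's laboratory work, so a site working from them would not collect the pregnancy test. The required chemistry draw does not bring it in, because βhCG is a separate analyte. The addendum's general clause does include it, but as a conditional item, and the narrower list is attached to the same document.

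Pregnancy is a mandatory reason to stop study treatment (protocol 8.8), and 9.5.4 calls for immediate withdrawal from treatment once it is confirmed. The scheduled test is what finds a pregnancy nobody suspects; the testing in 9.5.4 depends on suspicion. If the scheduled test is skipped, weekly dosing continues until the next one. The memo asks for deviation entries only for missed efficacy measures. Neither document holds dosing for a missed pregnancy test, whereas protocol 8.5.4 holds it when platelet values are more than 14 days apart.

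The omission also fits badly with the rest of the guidance: the same assay is kept at Week 39 and left out at Week 52.

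**Working it through.** The documents state no count or interval for this test, so there is no figure to reproduce. The inputs are the pregnancy-test row and footnotes of protocol Appendix A, Appendix B, the memo and the addendum. Table marks with a trailing letter are read as a mark carrying footnote 8 (off-site collection).

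**1. Laboratory rows at Week 26/52 visits against the memo**

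| Protocol Appendix A row | Memo status at a remote visit |
|---|---|
| Chemistry, hematology, urinalysis (3) | Required |
| Thyroid, coagulation, retinol, hs-CRP, PD panel, NT-proBNP, immunogenicity, PK trough (8) | Requested where feasible |
| Pregnancy test (1) | Not named |

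That is 3 + 8 + 1 = 12 rows. The additional platelet and creatinine collections have their own schedule, which the memo keeps. Only the pregnancy test is unplaced.

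**2. Scheduled tests, in study weeks** (Y4-W26 = 156 + 26 = 182, and so on)

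- Week 26/52 visits: 78, 104, 130, 156, 182, 208, 234, 260, which is 8 tests.
- Week 13/39 visits: 91, 117, 143, 195, 221, 247, which is 6 tests, all kept by the memo.
- Total on treatment in Years 2 to 5: 8 + 6 = 14. W65 and Y4-W13 have no mark.

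**3. Which tests could fall after the memo**

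The documents give no last enrollment date, so this step is an inference. It assumes the usual limit of 4 weeks between studies.

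- Last parent-study end of treatment taken as 15 Sep 2017 (the safety-update cutoff in SAP 5.2): Day 1 by 13 Oct 2017, so W78 (Day 540) by 5 Apr 2019, W104 (Day 722) by 4 Oct 2019 and W130 (Day 904) by 3 Apr 2020.
- Taken as late as the SAP version 2.0 date, 9 Feb 2018: Day 1 by 9 Mar 2018, so W78 by 30 Aug 2019 and W104 by 28 Feb 2020, or 9 Mar 2020 with the 10-day window.

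Under both bounds W78 and W104 precede 17 March 2020. That leaves 10 tests from W130 on: six at Week 26/52 visits (130, 156, 182, 208, 234, 260) and four at Week 13/39 visits (143, 195, 221, 247). For the target day to fall on or after the memo date, W130 needs Day 1 on or after 26 Sep 2017, W156 on or after 28 Mar 2017, and Y4-W26 on or after 27 Sep 2016.

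**4. Interval when a test is missed** (next test minus previous test)

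| Missed | Scheduled interval ending at that test | Resulting interval |
|---|---|---|
| W130 | 13 | 143 − 117 = 26 |
| W156 | 13 | 182 − 143 = 39 |
| Y4-W26 | 26 | 195 − 156 = 39 |
| Y4-W52 | 13 | 221 − 195 = 26 |
| Y5-W26 | 13 | 247 − 221 = 26 |
| Y5-W52 | 13 | 273 − 247 = 26 (to the post-treatment visit) |
| W156 and Y4-W26 | – | 195 − 143 = 52 |

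The schedule's own longest interval in this span is 26 weeks (W52 to W78, and W156 to Y4-W26). If the blank Y4-W13 cell should hold a test (week 169), the intervals are 169 − 143 = 26 and 195 − 169 = 26, and nothing exceeds 26 weeks.

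**The case against.** The strongest reply is that the addendum is later and broader, and that its general clause already calls for the test whenever collection is feasible. Since blood is drawn at the remote visit, that condition should normally be met. On this view the problem is a mismatch between two texts. This largely stands, and it rules out a stronger reading that a reader might take from the memo: that the pregnancy test was waived. No text waives it. What remains is that the addendum makes the test conditional and carries the memo's narrower list with it.

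A reader might also infer from the schedule that 8 of 14 tests are lost. The count is right for Years 2 to 5 as a whole, but it includes W78 and W104, which on the inferred dates came before the memo. The measure is also renewed month by month and applies only to visits actually held remotely, so no patient is shown to lose eight tests, or even six.

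Third, most of the consequence lies within intervals the protocol already accepts. That stands for four of the six tests, and Y5-W52 falls at the end of dosing with a post-treatment test to follow.

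Fourth, other safeguards continue: the Week 13/39 tests, testing of any suspected pregnancy (9.5.4), two or more contraceptive methods for female patients (6.3.1) and the telephone contact. The number of women concerned is not stated and could be very small. The monthly updates are not among the documents, so one of them may have added the test.

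Finally, requiring core safety tests and making the rest depend on feasibility is ordinary practice in a pandemic. That explains the tiers, but not why this one scheduled safety test is in neither.

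**Conclusion.** The point holds as a limited safety gap in the wording of the remote-visit guidance. The memo omits a scheduled test and the addendum restores it only conditionally, although the same test remains in force at Week 13/39 visits. At most the six Week 26/52 tests from W130 on, of ten scheduled, could be affected. The number is smaller for any one patient, and only women of childbearing potential at the Argentine and Brazilian sites with a remote visit are concerned.

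A single miss usually gives 26 weeks, which is no worse than the existing longest gap. Only W156 or Y4-W26 leads to 39 weeks. The 52-week figure should not be read as typical: it needs Day 1 on or after about 28 March 2017, two remote visits 26 weeks apart, and no test at either.

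The omission itself is plain from the text. The six-of-ten figure rests on the inferred dates, and the 39- and 52-week figures rest on reading the blank Y4-W13 cell as no test. The change is worth making because it is cheap and concerns an event that ends treatment; the documents do not show that any patient was harmed or went untested.

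**What to change.** Add the pregnancy test (serum βhCG, females of childbearing potential) to the required specimens for remote Week 26 and Week 52 visits, next to serum chemistry, hematology and urinalysis. Make the change in the addendum and in the next update of the memo, so that the two agree. Footnote 7 of the schedule already specifies the assay for these visits, and footnote 8 already allows off-site collection of it at Week 13/39 visits. All scheduled tests would then stay required and the longest scheduled gap would remain 26 weeks.

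The cost is one phrase in each document and one extra assay for a subset of patients, at a visit where blood is already drawn. The documents do not describe tube or shipping requirements, so the sponsor should confirm with the laboratory that the same draw can serve.

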The purpose of this supplement (to the global study protocol) is to fulfill MHRA requirements. The following changes will be made to the protocol:

1. The term "abstinence" will be further defined as "true abstinence" i.e., when this is in line with the preferred and usual lifestyle of the subject. Periodic abstinence (e.g., calendar, ovulation, symptothermal, post-ovulation methods), declaration of abstinence for the duration of a trial, and withdrawal are not acceptable methods of contraception."

The following table provides a summary list of the modifications to the protocol.

List of Protocol Modifications

Section	Modification	Rationale
Protocol Synopsis; Section 5.1 Inclusion Criteria #3 a and b	 Was: 3. Satisfy one of the following: a Females: Non-pregnant and non-lactating; surgically sterile, postmenopausal, abstinent, or if engaged in sexual relations of childbearing potential, patient is using an acceptable contraceptive method (refer to Section 6.3.1) from the time of signing the informed consent form until at least 3 months after the last dose of ISIS 420915. b. Males: Surgically sterile, abstinent, or if engaged in sexual relations with a female of childbearing potential, patient is utilizing an acceptable contraceptive method (refer to Section 6.3.1) during and for 3 months after the last dose of ISIS 420915. 	The definition of abstinence as "true abstinence" is needed per the long duration of the clinical trial.

List of Protocol Modifications *Continued*

Section	Modification	Rationale
	 Is: 3. Satisfy 1 of the following: a. Females: Non-pregnant and non-lactating; surgically sterile, postmenopausal, abstinent*, or if engaged in sexual relations of childbearing potential, patient is using an acceptable contraceptive method (refer to Section 6.3.1) from the time of signing the informed consent form until at least 3 months after the last dose of ISIS 420915. b. Males: Surgically sterile, abstinent*, or if engaged in sexual relations with a female of childbearing potential, patient is utilizing an acceptable contraceptive method (refer to Section 6.3.1) during and for 3 months after the last dose of ISIS 420915. 	

12.4	Study Monitoring	54
12.5	Language	55
12.6	Compensation for Injury	55
13. F	REFERENCES	56
14. A	APPENDICES	58
Apper	ndix A Schedule of Procedures	59
Apper	ndix B List of Laboratory Analytes	67
Apper	ndix C Additional Visits for Platelet and Serum Creatinine	69
	TABLE OF TABLES	Page
Table 1	Study Drug Characteristics	33
	TABLE OF FIGURES	
		Page
Figure 1	Design of Chimeric 2'-MOE Phosphorothioate Oligonucleotides (MOE-Gapmer). The sequence of ISIS 420915 is shown	

PROTOCOL AMENDMENT

Protocol Number: ISIS 420915-CS3

Protocol Title: An Open-Label Extension Study to Assess the Long-Term Safety

and Efficacy of ISIS 420915 in Patients with Familial Amyloid

Polyneuropathy (FAP)

Amendment Number: 5

Amendment Date: 22 Feburary 2017

The main purpose of this amendment is to provide the opportunity for patients to receive a fourth and fifth year of treatment with a modified assessment schedule if at the end of 3 years of treatment ISIS 420915 is not commercially available in the country of the patient.

Minor changes (not included in the list of changes below) have been made throughout the protocol to correct errors and/or to improve the overall clarity of the original protocol but these changes do not impact subject safety, exposure, or the overall study design.

The following table provides a summary list of major changes to the protocol; added text in underlined bold, deleted text in strikethrough:

Protocol Section	Description of Change	Rationale
Synopsis	If at the end of 3 years of treatment,	To provide the opportunity for patients to
3.1 Study Design	ISIS 420915 is not commercially available in the country of the patient, the patient	receive a fourth and fifth year of treatment if at the end of 3 years of
2.4.2 Doot Transferent	may continue to receive treatment in this	treatment, ISIS 420915 is not
3.4.3 Post-Treatment	study for up to 2 years more or until	commercially available in the country of
	ISIS 420915 becomes commercially	the patient.
	available in the patient's country,	uio pauoii.
	whichever occurs earlier. At the end of	
	the 5 years of treatment with ISIS 420915	
	in this study, if ISIS 420915 is not	
	commercially available, patients may be	
	allowed to continue receiving treatment	
	with ISIS 420915 via an early access route	
	to be defined by the Sponsor and	
	depending on local regulations. After	
	completing the treatment period, patients will	
	enter the 3-month post-treatment evaluation	
	period. If a patient discontinues treatment	
	in this study, but is continuing to receive	
	treatment with ISIS 420915 via another	
	mechanism, the entry of the patient into	
	the 3-month post-treatment evaluation	
	period may be omitted. Alternatively, after completing the 3 year treatment period (Week	
	156 visit), a patient may be offered the	
	opportunity to continue to receive ISIS	
	opporturity to continuo to receive 1313	

Protocol Section	Description of Change	Rationale
Synopsis 3.1 Study Design 3.4.3 Post-Treatment Continued	420915. Continuation of ISIS 420915 may eccur via early access, a separate open label extension protocol, or other programs depending on local regulations. Patients may continue to receive treatment via 1 of these mechanisms until ONE (1) of the following is met: - ISIS 420915 is commercially available in the local country; or - ISIS 420915 is rejected by the regulatory authority in the local country, or Spensor terminates access to ISIS 420915 for reasons including, but not limited to safety issues or emergent data	
Synopsis Study Design and Treatment Schema 3.4.3 Post-Treatment 6.1.3 Post-Treatment Period	If a patient discontinues treatment in this study, but will continue to receive treatment with ISIS 420915 via another mechanism, the entry of the patient into the 3-month post-treatment evaluation period may be omitted.	To avoid interruptions in therapy.
Synopsis Study Design and Treatment Schema 2.4 Rationale for Dose and Schedule of Administration 3.4 Overall Study Duration and Follow-up 3.4.2 Treatment 8.1 Study Drug Administration Appendix A Appendix C	Treatment period up to 5 years (Week 1 up to Y5-W52)	To provide the opportunity for patients to receive a fourth and fifth year of treatment if at the end of 3 years of treatment, ISIS 420915 is not available in the country of the patient.
Study Design and Treatment Schema Appendix A Appendix C	Post-treatment evaluation period is 3 months from last dose	To provide flexibility, applicable to early terminations as well as completing Year 3 or Year 5 of treatment.
Synopsis 3.4.2 Treatment 6.1.2 Treatment Period	During the treatment period patients will report to the Study Center for evaluation and tests 95 times in year 1 (Weeks 1, 7, 13, 26, 52), and 2 times in each subsequent year (26th and 52nd week of each year).	Language modified to provide generic description for Years 2-5.

Protocol Section	Description of Change	Rationale
Synopsis 6.1.2 Treatment Period	There are 428 non-clinic visits (Weeks 4, 10, 15, 18, 21, 23, 29, 39) in Year 1 and 2 in each subsequent year (13 th and 39 th week of each year), where labs will be collected by the Sponsor-appointed home healthcare service or the Study Center as arranged by the Study Center personnel or by local laboratory with prior Sponsor approval.	Language modified to provide generic description for Years 2-5.
6.1.2 Treatment Period Appendix A	The mNIS+7 assessment and Norfolk QOL DN questionnaire are will be conducted at Weeks 26, 52, 78, 104, 130, and 156. The NIS assessment is conducted at Y4-W52 and Y5-W52. The Norfolk QOL-DN questionnaire is conducted at Weeks 26, 52, 78, 104, 130, and 156 as well as Y4-W52 and Y5-W52.	Language modified to provide generic description for Years 2-5.
6.1.2 Treatment Period 8.5.3 Safety Monitoring Rules for Ocular Effects	During the treatment period, an ophthalmology examination will be performed at Weeks 26, 52, 78, 104, 130, 156 and 2 times in each subsequent year (26 th and 52 nd week of each year).	Language modified to provide generic description for Years 2-5.
8.9 Withdrawal of Patients from the Study	Other reasons for withdrawal of patients from the study might include: • At the discretion of the Investigator or Sponsor for medical reasons • At the discretion of the Investigator or Sponsor for noncompliance • Significant protocol deviation • Administrative decision by the Investigator or Sponsor • ISIS 420915 becomes commercially available in the local country (patients in Year 4 or Year 5) • ISIS 420915 is rejected by the regulatory authority in the local country	Language modified to include alternative reasons for withdrawal.
10.1.2 Efficacy Endpoints	Change in the NIS score and components from baseline to Y5-W52 and Y4-W52 Change in the Norfolk QOL-DN questionnaire scores from baseline to Week 78 and Week 156 and at the end of each subsequent treatment year (52nd week of each year) Change in PND score from baseline to Week 78 and Week 156 and at the end of each subsequent treatment year (52nd week of each year) Change in GLS by ECHO from baseline to Week 78 and Week 156 and at the end of each subsequent treatment year (52nd week of each year) in the ISIS 420915-CS2 ECHO subgroup and in the Cardiomyopathy-ECHO (CM-ECHO) Set	Language modified to provide generic description for Years 2-5 and to reflect the change of NIS score as an efficacy measure in the study

Protocol Section	Description of Change	Rationale
10.1.3 Pharmacodynamic Endpoints 10.6.5 Pharmacodynamic Analysis	 Change from baseline in TTR level to Week 78 and Week 156 and at the end of each subsequent treatment year (52nd week of each year) Change from baseline in RBP4 level to Week 78 and Week 156 and at the end of each subsequent treatment year (52nd week of each year) 	Language modified to provide generic description for Years 2-5.
10.1.5 Exploratory Efficacy Endpoints	 Change in the ECHO parameters (except GLS) in the ISIS 420915-CS2 ECHO subgroup and in the Cardiomyopathy-ECHO (CM-ECHO) Set from baseline to Week 78 and Week 156 and at the end of each subsequent treatment year (52nd week of each year) Change in NT-proBNP from baseline to Week 78 and Week 156 and at the end of each subsequent treatment year and at the end of each subsequent treatment year (52nd week of each year) Change in the SF-36 questionnaire scores from baseline to Week 78 and Week 156 and at the end of each subsequent treatment year (52nd week of each year) 	Language modified to provide generic description for Years 2-5.
10.3 Populations	The CM-ECHO set will include the subset of the safety set that has 420915-CS2 Randomized Set that had a diagnosis of TTR cardiomyopathy at least 1 evaluable post baseline study entry of the parent study, but are not in the ECHO Subgroup in the parent study, plus patients who qualified to participate in the ECHO Subgroup (whether consented or not). Patients who did not meet the criteria for the ECHO assessment and Subgroup or the CM-ECHO Set in ISIS 420915-CS2, but who are found to meet those criteria upon entry into ISIS 420915-CS3, may also be included in additional analysis will include patients that participated in the ISIS 420915 CS2 ECHO subgroup plus those patients that did not participate in the ECHO subgroup but who had a diagnosis of TTR cardiomyopathy at ISIS 420915 CS2 study entry. Patients who did not meet criteria for the ECHO Subgroup or the CM ECHO Set in ISIS 420915 CS2, but who are found to meet those criteria upon entry into ISIS 420915-CS3, may also be included in additional analyses (details will be found in the SAP).	Updated language to be consistent with SAP.

Protocol Section	Description of Change	Rationale
10.4 Definition of Baseline	For safety, baseline for patients on active treatment in the parent study will be the parent study baseline. For patients on placebo in the parent study, baseline for safety will be the last non-missing assessment prior to the first dose of ISIS 420915 in this study (Study Day 1) (details will be found in the SAP). The Day 1 pre dose value in this study For efficacy, 2 baselines are defined for each patient: the parent study baseline and the baseline assessment in this study (details will be found in the SAP). The baseline for this study is defined as the End of Treatment assessment in the parent study (EOT Week 66 assessment). Further details of which assessments will be considered baseline for Echo analyses for this study will be included in the SAP. The baselines for additional analyses can be found in the SAP.	Updated language to be consistent with SAP.
Synopsis 10.6.3 Efficacy Analysis	Change from baseline to Week 78 and Week 156 and at Week 52 of each subsequent treatment year will be summarized by treatment group of the parent study for the following efficacy measures: mNIS+7 score; NIS score; Norfolk QOL DN (total score, symptoms domain score for Stage 1 patients, and physical functioning/large fiber neuropathy domain score for Stage 2 patients); mBMI and BMI; components of the mNIS+7 (NIS, heat-pain sensory, touch-pressure sensory, nerve conduction and heart rate to deep breathing tests); and PND score; and the following exploratory measures: ECHO parameters, NT-proBNP, and SF-36 questionnaire.	To reflect the change of NIS score as an efficacy measure in the study.
Appendix A Appendix C	 Added schedule for Year 4 and Year 5 Visit Window was increased to +/- 14 days aside from early termination visit ERG exam is not performed Body Weight (fasting) is not performed Immunogenicity is only performed once a year PK trough is performed 3 times a year Transthoracic ECHO is not performed and is not performed at the early termination visit if early termination is from Year 4-5 treatment NIS is substituted for mNIS+7 and performed once per year NIS is performed if early termination is from Year 4-5 treatment instead of mNIS+7 Norfolk QOL-DN, SF-36 Questionnaire, and PND Score are performed once per year 	Maintain safety schedule, simplify efficacy schedule.

PROTOCOL SYNOPSIS

Protocol Title	An Open-Label Extension Study to Assess the Long-Term Safety and Efficacy of ISIS 420915 in Patients with Familial Amyloid Polyneuropathy
Otrodo Phase	(FAP)
Study Phase	3
Indication	Familial Amyloid Polyneuropathy
Primary Objective	To evaluate the safety and tolerability of extended dosing with ISIS 420915 in patients with Familial Amyloid Polyneuropathy
Secondary Objectives	To evaluate the efficacy of extended dosing with ISIS 420915, based on change from baseline and progression rates, if applicable, in the following measures: • Modified Neuropathy Impairment Score +7 (mNIS+7) • Norfolk Quality of Life-Diabetic Neuropathy (Norfolk QOL-DN) questionnaire: • total score (all patients) • symptoms domain score (Stage 1 patients) • physical functioning/large fiber neuropathy domain score (Stage 2 patients) • Modified body mass index (mBMI) and body mass index (BMI) • NIS, heat-pain sensory, touch-pressure sensory, nerve conduction and heart rate to deep breathing tests (components of mNIS+7) • Polyneuropathy disability score (PND) • Global longitudinal strain (GLS) by echocardiogram (ECHO) in the ISIS 420915-CS2 ECHO subgroup and in the Cardiomyopathy-ECHO (CM-ECHO) Set To evaluate the pharmacodynamic (PD) effect of extended dosing with ISIS 420915 based on change from baseline in transthyretin (TTR) and
	retinol binding protein 4 (RBP4) To evaluate the plasma trough levels of ISIS 420915
Exploratory Objective(s)	To evaluate the change from baseline in the following measures: ECHO parameters (except GLS) in the ISIS 420915-CS2 ECHO subgroup and in the Cardiomyopathy-ECHO (CM-ECHO) Set Plasma N-terminal prohormone of brain natriuretic peptide (NT-proBNP) SF-36 questionnaire
Study Design	This is a multicenter open-label study. Eligible patients who have satisfactorily completed ISIS 420915-CS2 will receive 300 mg ISIS 420915 once weekly for 156 weeks (3 years). Patients will also receive supplemental doses of the recommended daily allowance of vitamin A. If at the end of 3 years of treatment, ISIS 420915 is not commercially available in the country of the patient, the patient may continue to receive treatment in this study for up to 2 years more or until ISIS 420915 becomes commercially available in the patient's country, whichever occurs earlier. At the end of the 5 years of treatment with ISIS 420915 in this study, if ISIS 420915 is not commercially available, patients may be allowed to continue receiving treatment with ISIS 420915 via an early access route to be defined by the Sponsor and depending on local regulations. After completing the treatment period, patients will enter the 3-month post-treatment evaluation period. If a patient discontinues treatment in this study, but is continuing to receive treatment with ISIS 420915 via another mechanism, the entry of the patient into the 3-month post-treatment evaluation period may be omitted.
Number of Patients	Approximately 135 patients may be eligible to enroll in this study

PROTOCOL SYNOPSIS Continued

Study Population	Inclusion Criteria:
	Completion of ISIS 420915-CS2 treatment with the following as judged by the Investigator and Sponsor:
	a. Satisfactory completion of dosing and EOT efficacy assessments
	b. No significant tolerability issues
	 c. Satisfactory compliance to the ISIS 420915-CS2 protocol requirements
	Under special circumstances, patients that participated in ISIS 420915-CS2 but did not complete the full treatment period may be allowed to participate in this study with approval from the Sponsor.
	Willingness to take vitamin A supplement
	3. Satisfy 1 of the following:
	Females: non-pregnant and non-lactating; surgically sterile, postmenopausal, abstinent, or if engaged in sexual relations of childbearing potential, patient is using an acceptable contraceptive method from the time of signing the informed consent form until at least 3 months after the last dose of ISIS 420915
	 Males: Surgically sterile, abstinent, or if engaged in sexual relations with a female of childbearing potential, patient is utilizing an acceptable contraceptive method during and for 3 months after the last dose of ISIS 420915
	Must have given written informed consent (signed and dated) and any authorization required by local law and be able to comply with all study requirements Exclusion Criteria:
	Have any new condition or worsening of existing condition that in the opinion of the Investigator or Sponsor would make the patient unsuitable for enrollment, or could interfere with the patient participating in or completing the study
Treatment Groups	All patients will receive 300 mg ISIS 420915 given once weekly. However, patients that had a dose reduction or schedule change in ISIS 420915-CS2 may continue with the same dose or schedule in this study.
Study Drug Dosage and Administration	ISIS 420915 will be administered as a weekly subcutaneous (SC) injection.
Rationale for Dose and Schedule Selection	This is the same dose and schedule used during Weeks 2 to 65 in the ISIS 420915-CS2 study.
Study Visit Schedule and Procedures	For an individual patient, a maximum period of 4 weeks is allowed between a patient's last dose in ISIS 420915-CS2 (CS2 Week 65 Visit) and initiation of dosing in this study (CS3 Day 1 visit). Periods longer than 4 weeks may be considered after discussion and approval by the Study Medical Monitor. However, the intention is to minimize the treatment pause between the two studies. Ideally, the first dose in this study should be administered 1-week after the last dose in ISIS 420915-CS2.
	The study for an individual patient will generally consist of the following periods:
	A ≤ 4-week screening period
	A 3 to 5-year treatment period during which ISIS 420915 will be administered as a once weekly SC injection
	A 3-month post-treatment evaluation period

PROTOCOL SYNOPSIS Continued

Study Visit Schedule and Procedures Continued

Screening Period:

A period of ≤ 4 weeks is allowed to complete the screening procedures outlined in the schedule of procedures in Appendix A. Safety clinical laboratory parameters and assessments from the ISIS 420915-CS2 study may be used for screening evaluation provided that they were taken within 4 weeks of Day 1. Periods longer than 4 weeks may be considered after discussion and approval by the Study Medical Monitor.

Treatment Period:

During the treatment period patients will report to the Study Center for evaluation and tests 5 times in Year 1 (Weeks 1, 7, 13, 26, 52) and 2 times in each subsequent year (26th and 52nd week of each year). Physical examination, collection of blood for measurement of safety clinical laboratory parameters and specialty labs, measurement of vital signs, and collection of adverse events and concomitant medication/procedure information will be performed according to the schedule of procedures in Appendix A. The following assessments will also be performed at specified visits during the study: mNIS+7, NIS, Norfolk QOL-DN questionnaire, SF-36 questionnaire, PND score, body weight, ophthalmology examination, electroretinogram (ERG), electrocardiogram (ECG), and transthoracic ECHO examination.

There are 8 non-clinic visits in Year 1 (Weeks 4, 10, 15, 18, 21, 23, 29, 39) and 2 in each subsequent year (13th and 39th week of each year) where labs will be collected by the Sponsor appointed home healthcare service or the Study Center as arranged by the Study Center personnel or by local laboratory with prior Sponsor approval. In addition, platelets will be collected weekly and serum creatinine every 2-3 weeks (Appendices A and C). Patients may also be contacted by phone to collect adverse events, concomitant medication and concomitant procedure information (Appendix A).

Patients may be provided with prefilled syringes, when available in each country. Once available a patient preference questionnaire may be conducted.

ISIS 420915 will be administered by either the Study Center personnel or at home by the patient/caregiver.

In order to ensure maintenance of the study blind in ISIS 420915-CS2, TTR, RBP4, retinol, and NT-proBNP from the first 13 weeks of treatment in this study will not be available to the Sponsor, Investigators, Study Center Personnel, or the patients until the ISIS 420915-CS2 study is unblinded.

[figure not shown]
Post-Treatment Evaluation Period:

After discontinuation of treatment with ISIS 420915 patients will enter a 3-month post-treatment evaluation period as outlined in the Schedule of Procedures in Appendix A and C. If a patient discontinues treatment in this study, but is continuing to receive treatment with ISIS 420915 via another mechanism, the entry of the patient into the 3-month post-treatment evaluation period may be omitted.

PROTOCOL SYNOPSIS Continued

